Participants may have up to 2 dose modifications of MK-8353 and selumetinib throughout the course of the study, as described in [Table 7](#). If further toxicity occurs or the criteria for resuming treatment are not met, the participant must be discontinued from the study treatment. If a participant experiences several toxicities and there are conflicting recommendations, follow the most conservative dose adjustment recommended (dose reduction appropriate to the most severe toxicity).

Exceptional circumstances to following the dose modification tables below may be considered after consultation with the Sponsor.

Table 7 MK-8353 and Selumetinib Dose Modification and Treatment Discontinuation Guidelines for Drug-Related Adverse Events

Eye disorders – Retinal Events (including serous detachment of the retina)	
Grade 1	Maintain dose level of MK-8353 and selumetinib and repeat ophthalmic monitoring including visual acuity assessment and ocular coherence tomography (OCT) within 10 days.
Grade 2	Interrupt MK-8353 and selumetinib dosing and refer the participant to ophthalmologist within 1 week and obtain OCT within 10 days: If resolved to baseline or Grade $\leq 1$ within 10 days, resume treatment at current dose level and continue schedule of visual assessments established per protocol. If not resolved to baseline or Grade $\leq 1$ within 10 days, resume treatment at reduced dose level and continue the schedule of events of visual assessments established per protocol.
Grade 3	Interrupt MK-8353 and selumetinib and refer the participant to ophthalmologist within 1 week and obtain OCT: If resolved to baseline or Grade $\leq 1$ within 7 days, resume treatment at a reduced dose level and continue schedule of visual assessments established per protocol. If not resolved to baseline or Grade $\leq 1$ within 7 days, continue to hold the MK-8353 and selumetinib dose and repeat ophthalmic assessment in 10 days. If resolved to baseline or Grade $\leq 1$ , resume treatment at reduced dose level and continue schedule of visual assessments established per protocol. If remains Grade 3, permanently discontinue MK-8353 and selumetinib.
Grade 4	Permanently discontinue MK-8353 and selumetinib and immediately follow up with ophthalmic monitoring.
Eye disorder – Retinal Vein Occlusion (RVO)	
Any Grade	Permanently discontinue MK-8353 and selumetinib.
Other Eye Disorders (ie, Non-retinal Events)	

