Grade 1-2	Maintain dose level of MK-8353 and selumetinib and increase frequency of ophthalmic monitoring to at least 14 days until stabilization or resolution.
Grade 3	Interrupt MK-8353 and selumetinib and refer participant to ophthalmologist within 1 week: If resolved to Grade $\leq 1$ in $\leq 21$ days, reduce 1 dose level of MK-8353 and selumetinib. If not resolved to Grade $\leq 1$ in $\leq 21$ days, permanently discontinue MK-8353 and selumetinib.
Grade 4	Permanently discontinue MK-8353 and selumetinib.

Liver-related Adverse Events	
Grade 1 AST or ALT (> ULN - 3 × ULN)	Maintain dose level of MK-8353 and selumetinib.
Grade 2 AST or ALT (>3 - 5.0 × ULN) or 3 × baseline value (if liver metastasis) AND blood bilirubin ≤2.0 × ULN	Interrupt dose of MK-8353 and selumetinib until resolved to Grade ≤1 (or Grade ≤2 in case of liver metastasis), then: 
 
• If resolved in ≤14 days, maintain dose level of MK-8353 and selumetinib.
 
• If resolved in >14 days, reduce dose level of MK-8353 and selumetinib.
 
 Recurrence: 
 
• Interrupt dosing of MK-8353 and selumetinib until resolved to Grade ≤1 (or Grade ≤2 in case of liver metastasis), then resume treatment at a reduced dose.
 

Grade 2 AST or ALT (> 3 - 5.0 × ULN) or 3 × baseline value (if liver metastasis) AND blood bilirubin > 2.0 × ULN	Interrupt dose of MK-8353 and selumetinib until resolved to Grade ≤1 (or Grade ≤2 in case of liver metastasis), then: 
 
• If resolved in ≤7 days, resume treatment at a reduced dose of MK-8353 and selumetinib.
 
• If not resolved in ≤7 days, permanently discontinue MK-8353 and selumetinib.
 

Grade 3 AST or ALT (>5.0 - 8.0 × ULN) AND blood bilirubin ≤2.0 × ULN	Interrupt dose of MK-8353 and selumetinib until resolved to Grade ≤1 (or Grade ≤2 in case of liver metastasis), then: 
 
• If resolved in ≤14 days, maintain dose level of MK-8353 and selumetinib.
 
• If resolved in >14 days, reduce dose level of MK-8353 and selumetinib.
 
 Recurrence: 
 
• Interrupt dosing of MK-8353 and selumetinib until resolved to Grade ≤1 (or Grade ≤2 in case of liver metastasis), then resume treatment at a reduced dose.
 

AST or ALT (>8 x ULN) AND blood bilirubin* ≤ 2.0 × ULN	Permanently discontinue MK-8353 and selumetinib.

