AST or ALT (>5.0 × ULN) AND blood bilirubin* >2.0 × ULN	Permanently discontinue MK-8353 and selumetinib.
AST or ALT Grade 4 (>20.0 × ULN)	Permanently discontinue MK-8353 and selumetinib.

Cardiac Disorders	
Left ventricular systolic dysfunction Asymptomatic decrease of >10% in LVEF compared to baseline and the LVEF is below the institution's lower limit of normal	
Interrupt dose of MK-8353 and selumetinib and repeat evaluation of LVEF within 2 weeks.
 
 
If the LVEF recovers (defined as LVEF <math>\geq 50\%</math> or <math>\geq</math>LLN and absolute decrease <math>\leq 10\%</math> compared to baseline) <math>\leq 3</math> weeks, reduce 1 dose level after approval of the Sponsor Medical Monitor. Monitor LVEF 2 weeks after restarting on MK-8353 and selumetinib, every 4 weeks for 12 weeks and subsequently as per protocol.
 
If the LVEF does not recover within 3 weeks, permanently discontinue participant from study treatment. Closely monitor LVEF until resolution (or 16 weeks).
 

Grade 3-4	Permanently discontinue participant from MK-8353 and selumetinib. Closely monitor LVEF until resolution (or 16 weeks).
CK Elevation	
Grade 1-2	
Continue treatment on same dose level. Ensure patient is adequately hydrated. Monitor closely CK and serum creatinine levels.                      (If total CK <math>\geq 3 \times</math> ULN, measure isoenzymes and myoglobin in blood and urine).

Grade 3 (>5.0 - 10.0 $\times$ ULN) without renal impairment (ie, serum creatinine $< 1.5 \times$ ULN or $1.5 \times$ baseline)	
If asymptomatic, maintain dose of MK-8353 and selumetinib. Monitor closely and measure isoenzymes and myoglobin in blood and urine.
 
If symptomatic (muscle pain/spasms or muscle weakness), interrupt dose of MK-8353 and selumetinib until resolved to CTCAE Grade <math>\leq 1</math> and monitor closely, then:
 
 
If resolved in <math>\leq 21</math> days, reduce 1 dose level of MK-8353 and selumetinib.
 
If resolved in <math>> 21</math> days, permanently discontinue MK-8353 and selumetinib.
 

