Grade 4 without renal impairment (ie, serum creatinine $< 1.5 \times$ ULN or $1.5 \times$ baseline)	
If asymptomatic, interrupt dose of MK-8353 and selumetinib and monitor closely. Ensure patient is adequately hydrated and monitor and measure isoenzymes and myoglobin in blood or urine, and serum creatinine.
 
 
If resolved in <math>\leq 21</math> days, reduce 1 dose level of MK-8353 and selumetinib.
 
If resolved in <math>> 21</math> days, permanently discontinue MK-8353 and selumetinib.
 
If symptomatic, permanently discontinue MK-8353 and selumetinib.
 
 
If symptomatic (muscle pain/spasms), permanently discontinue MK-8353 and selumetinib.

Grade 3 or 4 with renal impairment (ie, serum creatinine $\geq 1.5 \times$ ULN or $1.5 \times$ baseline)	
Interrupt MK-8353 and selumetinib dose until resolved to Grade <math>< 1</math> or baseline level. Ensure patient is adequately hydrated. Monitor isoenzymes and myoglobin in blood or urine, and serum creatinine, then:
 
 
If resolved in <math>\leq 21</math> days, reduce 1 dose level of MK-8353 and selumetinib.
 
If resolved in <math>> 21</math> days, permanently discontinue MK-8353 and selumetinib.
 
 
Recurrence:
 
 
Permanently discontinue MK-8353 and selumetinib
 

Rash	
Grade 1	Treatment with MK-8353 and selumetinib should be maintained at the current dose. Initiate prophylactic regimen if it was not already and monitor closely.
Grade 2	First occurrence: Treatment with MK-8353 and selumetinib should be maintained at the current dose and rash should be closely monitored. Initiate prophylactic regimen if it was not already started. Reassess within a maximum of two weeks. If rash worsens or does not improve, interrupt dosing until improvement to Grade $\leq 1$ . Resume treatment at the same dose level.  Second occurrence: Reassess within a maximum of 2 weeks. If rash worsens or does not improve, interrupt dosing until improvement to Grade $\leq 1$ . Resume treatment at a reduced dose level. Only one dose reduction is permitted.

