Grade 3-4	Permanently discontinue MK-8353 and selumetinib.
Venous Thromboembolism	
Uncomplicated DVT or PE	Withhold MK-8353 and selumetinib for up to 3 weeks. 
 
• If improved to Grade 0 or 1, resume at reduced dose.
 
• If not improved, permanently discontinue.
 

Life threatening PE	Permanently discontinue MK-8353 and selumetinib.
All other Adverse Events (suspected to be related)	
Grade 1-2	If the event is a persistent Grade 2 AE not responsive to a specific therapy, consider MK-8353 and selumetinib interruption or reduction.
Grade 3	For other AEs, interrupt MK-8353 and selumetinib until resolution to Grade $\leq$ 1 or to pre-treatment/baseline level. If the event resolves within 21 days, then MK-8353 and selumetinib may be restarted at a lower dose (one level below that previously received) based upon the Investigator's discretion.
Grade 4	Permanently discontinue study drug (MK-8353 and selumetinib).

AE = adverse event; ALT = alanine aminotransferase; AST = aspartate aminotransferase; CK = creatine kinase; CTCAE = Common Terminology Criteria for Adverse Events; LLN = lower limit of normal; LVEF = left ventricular ejection fraction; ULN = upper limit of normal

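### Table 7's CK rows with and without renal impairment overlap and give conflicting actions, and symptomatic Grade 4 CK is handled less strictly when renal impairment is present

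*Combined protocol and SAP*

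**What the plan says.** Section 6.6.4.1 makes Table 7 binding for both drugs. Under CK Elevation, the Grade 3 row and the Grade 4 row for participants "without renal impairment (ie, serum creatinine" set the condition as below 1.5 x ULN or 1.5 x baseline. A single third row, "Grade 3 or 4 with renal impairment (ie, serum creatinine", sets it as at or above 1.5 x ULN or 1.5 x baseline.

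The actions are:

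- Grade 3 without impairment, no symptoms: "If asymptomatic, maintain dose of MK-8353 and selumetinib".
- Grade 3 without impairment, with symptoms: interrupt to Grade 1 or lower; reduce one level if resolved within 21 days, otherwise stop.
- Grade 4 without impairment, no symptoms: interrupt, with the same 21-day rule.
- Grade 4 without impairment, with symptoms: "If symptomatic (muscle pain/spasms), permanently discontinue MK-8353 and selumetinib".
- Grade 3 or 4 with impairment, whatever the symptoms: "Interrupt MK-8353 and selumetinib dose until resolved to Grade" <1 (as printed) or baseline. Then reduce one level if resolved within 21 days, otherwise stop; stop on recurrence.

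The text ahead of Table 7 also gives a tie-breaker: "If a participant experiences several toxicities and there are conflicting recommendations, follow the most conservative dose adjustment recommended".

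**The concern.** Rows named as opposites should divide participants cleanly. Here both definitions join the same two limits with 'or', so some participants belong to both rows, and in two situations the rows give different instructions. Sites could then manage identical CK and creatinine results differently.

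A second problem does not depend on the overlap. A participant over both creatinine limits falls only in the renal-impairment row. With symptomatic Grade 4 CK, that participant may be re-treated at a reduced dose, whereas the same CK event with normal creatinine ends treatment. The plan gives no reason why added renal impairment should lead to the less strict action.

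**Working it through.** The plan states no figure to reproduce here; the check is one of logic.

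**Inputs.** Row conditions and actions are from Table 7. Table 3 (Section 5.1) admits participants with creatinine above 1.5 x ULN if clearance is at least 60 mL/min. Section 2.2.3.1 says that MK-8353 inhibits MATE1 and OCT2, and that these transporters account for about 10-40% of creatinine clearance.

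**Step 1: the overlap.** Let b = baseline/ULN and c = current creatinine/ULN.

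- Without impairment: c < 1.5 or c < 1.5b, that is, c < 1.5 x max(1, b).
- With impairment: c >= 1.5 or c >= 1.5b, that is, c >= 1.5 x min(1, b).
- Both: 1.5 x min(1, b) <= c < 1.5 x max(1, b).

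| Baseline (x ULN) | Creatinine meeting both rows (x ULN) |
|---|---|
| 0.5 | 0.75 to <1.5 |
| 0.7 | 1.05 to <1.5 |
| 0.9 | 1.35 to <1.5 |
| 1.0 | none |
| 1.2 | 1.5 to <1.8 |
| 1.6 | 1.5 to <2.4 |

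Two spot checks: b = 0.7 and c = 1.1 gives 1.1/0.7 = 1.57 x baseline but under 1.5 x ULN, so both rows apply. b = 1.4 and c = 1.6 is over 1.5 x ULN but only 1.6/1.4 = 1.14 x baseline, so again both apply. At b = 1.6, a participant with unchanged creatinine is already in both rows.

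**Step 2: the actions inside the overlap.**

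| CK event | Row without | Row with | Main action |
|---|---|---|---|
| Grade 3, asymptomatic | continue | interrupt, then reduce | conflict |
| Grade 3, symptomatic | interrupt, then reduce | interrupt, then reduce | same |
| Grade 4, asymptomatic | interrupt, then reduce | interrupt, then reduce | same |
| Grade 4, symptomatic | stop for good | interrupt, then reduce | conflict |

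That is two of four cells. The two matching cells still differ in the recovery target and in the recurrence rule, which only the row with impairment has.

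**Step 3: outside the overlap.** Take b = 0.7 and c = 1.6. This is over 1.5 x ULN and 1.6/0.7 = 2.29 x baseline, so only the row with impairment applies. Symptomatic Grade 4 CK may then restart at a reduced dose if it resolves within 21 days. At normal, unchanged creatinine only the other row applies, and treatment ends.

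**Step 4: can participants reach the overlap through the drug itself?** Assume creatinine is proportional to 1/clearance and, as an upper bound, that secretion is fully blocked (the actual block is not given). Creatinine would rise to 1/(1 - 0.10) = 1.11 up to 1/(1 - 0.40) = 1.67 x baseline. Reaching 1.5 x baseline needs a clearance loss of 1 - 1/1.5 = 33.3%, which is 0.333/0.40 = 83% block even at the top of the range. From b = 1.2, reaching 1.5 x ULN needs only 1.5/1.2 = 1.25, a 25% rise. So the route is possible, but hard for baselines at or below ULN.

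**Step 5: the repair.** The negation of (c >= 1.5 or c >= 1.5b) is (c < 1.5 and c < 1.5b). On a grid of 22 baselines (0.42 to 1.47) by 52 creatinine values (0.40 to 2.95), 1,144 pairs in all, the present wording puts 182 in both rows and none in neither. With 'and' in the rows without impairment, none is in both and none in neither. The grid is unweighted, so 182 is not an estimate of how often this happens.

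**The case against.** **The rows are evidently meant as complements, and 'or baseline' may be an alternative reference for some participants.** Probably so, but the reader cannot tell which way a one-limit crossing was meant to fall. Where Table 7 wants a baseline reference for a subgroup it says so, as in the liver rows: "baseline value (if liver metastasis) AND blood bilirubin". The CK rows carry no such condition.

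**The most-conservative rule already settles the conflict.** This is the best point. If a creatinine rise counts as a second toxicity, the rule gives the stricter action in many overlap cases, so it would be wrong to infer that every overlap case is left without guidance. But the rule is worded for several toxicities, and it does not fit a participant whose creatinine is unchanged from a baseline of 1.5 x ULN or more. Nor does it reach the case in Step 3, where one row applies and nothing conflicts.

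**Section 7.1 already protects participants.** It requires discontinuation for unacceptable adverse experiences, for unnecessary risk, and on the investigator's decision. These limit the consequence, and a reader should not infer that such participants must be re-treated. But they rest on judgement and do not correct the table.

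**The row with impairment is not lenient overall.** Correct. It interrupts asymptomatic Grade 3, its printed recovery target is tighter than that for symptomatic Grade 3 without impairment, and it stops treatment on recurrence. It is less strict in one cell of four.

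**Other Grade 4 events do not settle how CK should be handled.** A reader might argue from the rest of Table 7. Outside CK, eight of the nine rows labelled Grade 4 or Grade 3-4 end treatment, including the catch-all row, "Permanently discontinue study drug (MK-8353 and selumetinib"; diarrhea is the exception. The documents do not support that inference: CK has its own rows, and asymptomatic Grade 4 CK without impairment may also restart, so CK is treated differently in any case. The case for the change rests on the comparison within the CK rows.

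**Conclusion.** The CK rows are wrong as written. For any baseline other than exactly the ULN there is a creatinine range that meets both definitions, and within it two of four cells have conflicting main actions. Separately, symptomatic Grade 4 CK, and only that cell, is handled less strictly with renal impairment than without.

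The overlap rests on the literal 'or' in all three rows; the second problem does not. The documents give no CK frequency, so the number of participants affected is unknown.

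A reader might infer that the dose-escalation results are at risk. The documents do not support that. The sample size and mTPI rules do not use these rows. Many such events would already be DLTs under criterion 3 or 4 of Section 6.6.2, so any effect on DLT classification is a corner case. This is a participant-level safety correction that should be made.

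**What to change.** Two edits to the three CK rows of Table 7:

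1. In both rows without renal impairment, write <1.5 x ULN **and** <1.5 x baseline. The rows then become complements.
2. In the row with renal impairment, state that symptomatic Grade 4 CK is permanently discontinued.

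Make both together. Edit 1 alone would move symptomatic Grade 4 participants in the overlap into the row that allows restart.

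**Cost.** Beyond the wording, some participants with asymptomatic Grade 3 CK who might have continued will be interrupted and reduced, and stopped on recurrence. They include some whose creatinine rise comes from transporter inhibition and some whose baseline is already at or above 1.5 x ULN. Section 2.2.3.1 allows cystatin C from a 10% creatinine rise, which can be used to evaluate renal function in those with a rise. In Cycle 1 there are 3 x 4 x 2 = 24 scheduled doses of each drug. Missing 6 is 25.0% and does not exceed the 25% limit; missing 7 is 29.2%, which brings discontinuation under Section 7.1 and, if drug-related, a DLT under criterion 9. Edit 2 is a stricter clinical rule and needs the sponsor's clinical agreement.

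It is tempting to add that participants with baseline creatinine at or above 1.5 x ULN are classified by 1.5 x baseline only. I would not. It is not needed to remove the overlap, and it creates a new reversal: at creatinine 2.0 x ULN, a participant with baseline 1.4 would be with impairment (limit 1.5), while one with baseline 1.6 would be without (limit 1.5 x 1.6 = 2.4).

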## 6.6.4 Guidelines for Dose Modification Due to Adverse Events

### 6.6.4.1 Dose Modification for MK-8353 and Selumetinib

Adverse events (both nonserious and serious) associated with MK-8353 and selumetinib exposure may occur shortly after the first dose or several months after the last dose of treatment.

The CTCAE v4.0 must be used to grade the severity of AEs for individual participants. The investigator may attribute each toxicity event to MK-8353 alone, to selumetinib alone, or to the combination, but modification of the doses of both drugs must be followed according to [Table 7](#). Examples of dose reduction are as follows:

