Grade 3	First occurrence: Treatment with MK-8353 and selumetinib should be interrupted. Reassess the participant weekly. Consider referral to dermatologist and manage rash per dermatologist's recommendation. Interrupt treatment until improvement to Grade $\leq 1$ . Resume treatment with MK-8353 and selumetinib at a reduced dose level.  Second occurrence: Interrupt treatment until improvement to Grade $\leq 1$ . Resume treatment with MK-8353 and selumetinib at a reduced dose level. If participant is at the lowest dose, participant should be discontinued. Consider referral to dermatologist and manage rash per dermatologist's recommendation.
Grade 4	Permanently discontinue MK-8353 and selumetinib.
Diarrhea	
Uncomplicated Grade 1-2	Consider temporary interruption of MK-8353 and selumetinib until resolved to Grade $\leq 1$ . Treatment with MK-8353 and selumetinib may then be resumed at the same dose level.
Complicated Grade 1-2	Temporarily interrupt MK-8353 and selumetinib treatment until resolved to Grade $\leq 1$ . Restart MK-8353 and selumetinib at one reduced dose level. If participant is at the lowest dose, participant should be discontinued.
Grade 3-4	Temporarily interrupt MK-8353 and selumetinib treatment until resolved to Grade $\leq 1$ . Restart MK-8353 and selumetinib at a reduced dose level. If participant is at the lowest dose, participant should be discontinued.
Nausea/Vomiting	
Grade 1-2	Treatment with MK-8353 and selumetinib should be maintained at the current dose. Promptly institute antiemetic measure.
Grade 3	Temporarily interrupt MK-8353 and selumetinib treatment until resolved to Grade $\leq 1$ . Resume treatment with MK-8353 and selumetinib at the same dose if, in the judgment of the investigator, the toxicity is considered to be unrelated to selumetinib, or at one reduced dose level.  Note: Interrupt dose for $\geq$ Grade 3 vomiting or Grade 3 nausea only if the vomiting or nausea cannot be controlled with optimal antiemetics (as per local practice).
Grade 4	Permanently discontinue MK-8353 and selumetinib treatment

Interstitial Lung Disease/Pneumonitis	
Grade 1	Maintain dose level of MK-8353 and selumetinib. Monitor weekly.
Grade 2	Withhold MK-8353 and selumetinib for up to 3 weeks. 
 
• If improved to Grade 0 or 1, resume treatment at 1 reduced dose level of MK-8353 and selumetinib
 
• If not resolved within 3 weeks, permanently discontinue MK-8353 and selumetinib.
 

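### Table 7 lets both drugs restart at full dose after Grade 3 nausea or vomiting blamed on MK-8353 alone

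*Combined protocol and SAP*

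**What the plan says.** The title of Table 7 (Section 6.6.4.1) limits its scope: "Treatment Discontinuation Guidelines for Drug-Related Adverse Events". It covers both agents, and the section requires both drugs to be modified according to the table. The lead-in to that section also says: "The investigator may attribute each toxicity event to MK-8353 alone, to selumetinib alone, or to the combination".

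For Grade 3 nausea or vomiting, the table stops both drugs until the event falls to Grade 1 or better. Both then resume at the same dose if, in the investigator's judgment, "the toxicity is considered to be unrelated to selumetinib, or at one reduced dose level". A note limits the interruption to cases "only if the vomiting or nausea cannot be controlled with optimal antiemetics".

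Neighbouring rows read differently:

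- Grade 3–4 diarrhea: "Restart MK-8353 and selumetinib at a reduced dose level".
- Grade 3 rash: "Resume treatment with MK-8353 and selumetinib at a reduced dose level".
- Other related Grade 3 events that resolve within 21 days: both drugs "may be restarted at a lower dose (one level below that previously received"), at the investigator's discretion.

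**The concern.** The same-dose condition tests relatedness to one of the two study drugs. An event caused by neither drug lies outside a table for drug-related events. An event attributed to selumetinib or to the combination fails the condition. Within the table's scope, the branch therefore operates only when MK-8353 alone is blamed, and it then permits the suspected drug to come back unchanged.

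A participant whose Grade 3 vomiting has already resisted optimal antiemetics could thus restart at the MK-8353 dose thought to have caused it. The same event attributed to selumetinib or to the combination would mean restarting one level lower.

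**Working it through.** No plan figure needs reproducing. The check is a reading of the rule against the rest of the protocol, plus simple dose ratios.

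**Step 1. Outcome by attribution** (Grade 3 nausea or vomiting that meets the antiemetic note and has recovered to Grade 1 or better)

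| Attributed to | Action under Table 7 |
|---|---|
| Selumetinib alone | Both drugs one level lower |
| Combination | Both drugs one level lower |
| MK-8353 alone | Same dose of both permitted; reduction optional |
| Neither drug | Outside the table's scope |

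**Step 2. Is this row unusual?** I compared all Table 7 rows. None of the others makes its action depend on one named drug. Two other rows allow the same dose at Grade 3: AST/ALT elevation with bilirubin no more than 2 × ULN that resolves within 14 days, and asymptomatic CK elevation without renal impairment. Those depend on recovery time or symptoms, not on which drug is blamed.

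**Step 3. Does other text require a reduction?**

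- Section 5.6: continuing after a Cycle 1 DLT needs discussion with the Sponsor. No dose is specified.
- Section 6.6.2: DLTs count relatedness to study treatment, whichever drug is blamed. The nausea/vomiting exception in item 3 is worded for short events without antiemetic use. Taken literally, a related Cycle 1 event that fails antiemetics falls outside it and counts as a DLT. This does not fix the restart dose.
- Section 6.6.4.1: the most-conservative rule settles conflicts between several toxicities, not the attribution of one.
- Section 7.1: discontinuation follows a toxicity-related interruption of more than 14 consecutive days in Cycle 1, or more than 25% cumulative missed doses. Shorter interruptions remain under Table 7.
- Section 10.3.4: rechallenge after a serious, possibly related event, or where re-exposure adds significant risk, needs advance Sponsor approval. That approval follows the protocol's dose-modification guidelines and so leads back to this row.

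None of these requires a lower dose for an event attributed to MK-8353 alone.

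**Step 4. Size of the step not required** (MK-8353 dose levels from Section 4.3.3)

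Ratio = dose at same-dose restart ÷ dose one level lower:

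- 250/200 = 1.25
- 200/150 = 1.33
- 150/100 = 1.50
- 100/50 = 2.00

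**Step 5. Where the step would be discontinuation.** Example 3 in Section 6.6.4.1 discontinues a participant who needs a reduction when either drug is at its lowest dose (MK-8353 50 mg or selumetinib 25 mg). Among the seven diagonal levels this is DL1 only (1 of 7). Among the off-diagonal starting doses in Table 1, it is the two that follow a diagonal conclusion at DL2: 100/25 mg and 50/50 mg (MK-8353/selumetinib). Earlier reductions, or the additional dose levels that Section 4.3.4 allows, can also bring a participant there.

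**The case against.** The strongest counter-argument is that the branch will rarely be used. Section 10.3.4 makes attribution to the combination the default and accepts a single-agent attribution only when the data support it fully. The drugs are taken together on the same schedule (Section 6.6.3.1). Section 2.2.3.1 predicts that MK-8353 300 mg BID, above this study's 250 mg maximum, raises selumetinib AUC up to 1.6-fold. Calling vomiting unrelated to selumetinib would be hard to defend. This stands on frequency, but the same facts make that judgment a weak basis for waiving a reduction.

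Naming selumetinib may also be deliberate. Section 6.5.3.2 says nausea and vomiting have been reported with it, while Section 6.5.3.1 plans for them under MK-8353 without giving a rate. That may explain the wording, but it does not justify exempting an event already attributed to MK-8353.

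Table 7 also has no general rule that every related Grade 3 event lowers the dose, and this row permits a same-dose restart without mandating it. Both points are correct. The anomaly is narrower: the choice turns on attribution to one of two drugs.

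Finally, the ratios in Step 4 are just the dose ladder and measure no risk. The fix also lowers selumetinib, which the investigator has judged not to be the cause. Both points stand and bear on size and cost.

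**Conclusion.** The concern holds as a minor wording gap with a patient-safety consequence. For Grade 3 nausea or vomiting attributed to MK-8353 alone, the plan permits full-dose restart of both drugs and nothing elsewhere requires a reduction. Where this happens, MK-8353 restarts at 1.25 to 2.0 times the next lower dose, or treatment continues where a reduction would have meant discontinuation.

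The conclusion rests on the literal wording of the row and on sites sometimes using the single-agent attribution that the protocol allows. How often that would happen cannot be derived from the documents and should be uncommon. It does not contradict the rule that both drugs are modified together, since both still move together.

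**What to change.** In the Grade 3 nausea/vomiting row of Table 7, make the same-dose condition *unrelated to both MK-8353 and selumetinib*. Deleting the same-dose branch has the same effect within a table for drug-related events and is the tidier edit. Either way, an event that led to interruption and is related to either drug restarts one level lower.

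The drafting cost is a few words. The DLT definition and the mTPI rules do not change.

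The clinical cost falls on the few participants affected:

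- Selumetinib also steps down, although it was not blamed.
- The reduction uses part of a limited allowance: "Participants may have up to 2 dose modifications of MK-8353 and selumetinib throughout the course of the study".
- If either drug is at its lowest dose, the participant discontinues. The Grade 3–4 diarrhea row already accepts that consequence.
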